9.2.1. Inclusion Criteria

Patients must meet all of the following inclusion criteria to be eligible for inclusion in the study:

1. First hospital health claim with an administration of elranatamab on or after March 26, 2024.
2. Have a diagnosis of MM.
3. Aged ≥ 18 years at the time of first hospital claim for elranatamab (i.e., index date).

9.2.2. Exclusion Criteria

Patients meeting any of the following criteria will not be included in the study:

1. Evidence of administration of elranatamab as part of a clinical trial.

9.3. Variables

This section outlines patient exposure groups, variable definitions, and study endpoints to be reported across all study objectives. All codes for variable identification will be provided in the statistical analysis plan (SAP). The data source for all variables is Japan MDV.

9.3.1 Exposure Groups and Assessment Periods

[Table 1](#) outlines the variables to define exposure groups that will be used to identify patients and stratify analyses.

Table 1. Variables for Exposure

Variable	Role	Data Source	Operational Definition	
			Definition	Assessment Period(s)
Study population	Exposure	MDV	All patients with MM who have a hospital claim for elranatamab after March 26, 2024, and who meet the inclusion and exclusion criteria outlined in Sections 9.2.1 and 9.2.2.	Index date
SUD Exposure Group	Exposure	MDV	
Group A: Complete and timely SUD period
 
Patients in the study population with two 44mg/1.1mL vials (second 44mg/1.1mL vial is received 1 to 7 days after the first) and one subsequent 76mg/1.9mL vial between 1 to 7 days after second 44mg/1.1mL vial
 
Group B: Complete but not timely SUD period
 
Patients in the study population with two 44mg/1.1mL vials and one subsequent 76mg/1.9mL vial after the second 44mg/1.1mL vial, with one or both intervals between doses ranging from 8 to 14 days.
 
Group C: Alternative SUD period
 
 • Only one 44mg/1.1mL vial: patients in the study population with only one 44mg/1.1mL vial prior to receiving a 76mg/1.9mL vial • More than two 44mg/1.1mL vials: patients in the study population with more than 	SUD period

090177e1a4a71ff1\Approved\Approved On: 05-Nov-2025 14:15 (GMT)

Variable	Role	Data Source	Operational Definition	
			Definition	Assessment Period(s)
			
two 44mg/1.1mL vials prior to receiving a 76mg/1.9mL vial
 
 Extremely untimely: patients in the study population with more than 14 days between the first and second 44mg/1.1mL vial or between the second 44mg/1.1mL vial and the first 76mg/1.9mL vial 
Note that patients who received only 44mg/1.1mL vials or only 76mg/1.9mL vials are not classified under any SUD exposure group but will remain part of the study population.
	

Figure 2 illustrates possible elranatamab administration scenarios for each SUD group. These examples are not exhaustive and do not represent all potential administration schedules.

090177e1a4a71ff1\Approved\Approved On: 05-Nov-2025 14:15 (GMT)

Figure 2. SUD Periods Administration Schedule

[figure not shown]

Table 2 summarizes the patient exposure groups and assessment periods during which endpoints for each study objective will be measured. Patients will be included in the follow-up sub-period analyses if they have at least one claim for elranatamab or if the end date of their follow-up period falls within the sub-period's time frame.

Table 2. Patient Exposure Groups Stratification and Assessment Period for Study Objectives

Study Objective	Assessment period	Patient Exposure Groups
Objective 1 – Patient Characteristics	Baseline period	Study population
	Index date	Group A, Group A+B, Group C
Objective 2 – Treatment administration, dosing and timing	SUD period 
 Overall (Between first 44mg/1.1mL vial – first 76mg/1.9mL vial) Between first 44mg/1.1mL vial – second 44mg/1.1mL vial Between second 44mg/1.1mL vial – first 76mg/1.9mL vial 	Group A, Group A+B, Group C
	Follow-up period 
 Index date 	Study population

090177e1a4a71ff1\Approved\Approved On: 05-Nov-2025 14:15 (GMT)

Study Objective	Assessment period	Patient Exposure Groups
	
 • Index date (day 1) to day 8 • Day 9 to day 168 • Day 169 to end of follow-up period • Overall (day 1 to end of follow-up period) 	
Objective 3 – HCRU and costs	HCRU baseline assessment period	Study population
	SUD period 
 • Overall (Between first 44mg/1.1mL vial – first 76mg/1.9mL vial) • Between first 44mg/1.1mL vial – second 44mg/1.1mL vial • Between second 44mg/1.1mL vial – first 76mg/1.9mL vial 	Group A, Group A+B, Group C
	Follow-up period 
 • Index date • Index date (day 1) to day 8 • Day 9 to day 168 • Day 169 to end of follow-up period • Overall (day 1 to end of follow-up period) 	Study population
Objective 4 – Other MM treatments including supportive therapy	Follow-up period 
 • Index date • Index date (day 1) to day 8 • Day 9 to day 168 • Day 169 to end of follow-up period • Overall (day 1 to end of follow-up period) 	Study population
Objective 5 – Known adverse events	CRS/ICANS follow-up assessment period (CRS/ICANS events)	Group A, Group A+B, Group C
	SUD period (Cytopenia events) 
 • Overall (Between first 44mg/1.1mL vial – first 76mg/1.9mL vial) 	Group A, Group A+B, Group C

090177e1a4a71ff1Approved\Approved On: 05-Nov-2025 14:15 (GMT)

Study Objective	Assessment period	Patient Exposure Groups
	
 Between first 44mg/1.1mL vial – second 44mg/1.1mL vial Between second 44mg/1.1mL vial – first 76mg/1.9mL vial 	
Objective 6 – Infections	Follow-up period 
 Index date Index date (day 1) to day 8 Day 9 to day 168 Day 169 to end of follow-up period Overall (day 1 to end of follow-up period) 	Study population
Exploratory Objective 1 – Supportive medications	SUD period 
 Overall (Between first 44mg/1.1mL vial – first 76mg/1.9mL vial) Between first 44mg/1.1mL vial – second 44mg/1.1mL vial Between second 44mg/1.1mL vial – first 76mg/1.9mL vial 	Group A, Group A+B, Group C
	IVIG follow-up assessment period	Group A, Group A+B, Group C

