- **Study design:** This is a retrospective observational study utilizing de-identified data from Japan Hospital administrative claims data (Medical Data Vision [MDV]).
- **Population:** The study population will include all adults aged 18 years or older with an MM diagnosis who initiate elranatamab on or after March 26, 2024 (PMDA Elrexfio approval date). Patients with evidence of clinical trial participation will be excluded.
- **Variables:** The following variables will be summarized and reported:

Exposure of interest:

Exposure is defined as at least one record of a hospital claim for elranatamab on or after March 26, 2024. All patients included in the study will be considered exposed. Analyses of outcomes during the SUD period will also be stratified based on types of elranatamab exposure during that time (i.e., complete and timely SUD, complete but not timely SUD, alternative SUD). Clinical data will be collected from MDV hospital data.

Study outcomes:

Study endpoints include: elranatamab timing and dosing (i.e., types of doses, time between doses, relative administration intensity), HCRU and costs (i.e., IP/OP/ED claims and associated costs, degree of nursing), other MM treatment post elranatamab administration (i.e., PIs, SCT, supportive therapy), known adverse events (i.e., CRS events occurrence, frequency and associated length of stay, time from index to CRS event), infection (i.e., infection occurrence, time from index to infection, antibiotics), and supportive medication (i.e., IVIG, acetaminophen, dexamethasone).

Covariates:

Covariates will include baseline demographics (i.e., age, sex, weight etc.), and baseline clinical characteristics (i.e., comorbidities and treatment history).

- **Data sources:** The MDV database is a comprehensive resource containing administrative data from over 540 hospitals in Japan. This dataset includes information on demographics, mortality, labs, IP, OP, ED claims, treatments, procedures and costs of approximately 50 million patients. MDV is an aggregated, de-identified dataset where no patient can be individually identified and therefore no patient consent is required.
- **Study size:** This is a retrospective descriptive study with no a priori hypotheses; therefore, sample size calculations are not applicable. As of February 2025, MDV included 128 patients that had at least one hospital claim for an elranatamab administration.

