9.7. Data Analysis

All analysis will be descriptive in nature and no formal statistical comparisons will be performed between groups. All characteristics and endpoints will be reported separately for each assessment period and patient exposure groups of interest as defined in [Table 2. Patient Exposure Groups Stratification and Assessment Period for Study Objectives](#).

Raw data transferred by MDV will be reviewed for completeness, consistency and plausibility. Records with missing or implausible values (e.g., negative age, invalid dates) will be flagged and addressed according to predefined rules in the SAP. Duplicate records will be identified and removed. Variables will be derived and categorized as needed for analysis. Diagnosis and procedure codes will be mapped to standardized categories using the International Classification of Diseases, 10th revision (ICD-10) and Healthcare Common Procedure Coding System (HCPCS) classification systems. Missing data will be reported, and no imputation will be performed unless otherwise specified in the SAP.

Detailed methodology for summary and statistical analyses of data collected in this study will be documented in a SAP, which will be dated, filed, and maintained by the sponsor. The SAP may modify the plans outlined in the protocol; any major modifications of primary endpoint definitions or their analyses would be reflected in a protocol amendment.

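### CRS, ICANS, cytopenias and SUD supportive medication are reported only for patients who received a 76mg vial after a 44mg vial, so no estimate covers all elranatamab initiators

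*Protocol*

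**What the plan says.** Section 9.7 makes Table 2 the governing list: "All characteristics and endpoints will be reported separately for each assessment period and patient exposure groups of interest as defined in" Table 2. For Objective 5, that table assigns CRS and ICANS to a 14-day window from index and cytopenias to the SUD period, in both cases for Groups A, A+B and C. Exploratory Objective 1 has the same three groups, over the SUD period and, for IVIG, over 30 days from index. Objectives 1 to 4 and 6 each carry a Study population entry. Objective 5 and Exploratory Objective 1 do not.

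Table 1 defines the groups by vial sequence. Group A needs "one subsequent 76mg/1.9mL vial between 1 to 7 days after second 44mg/1.1mL vial". Group B needs "two 44mg/1.1mL vials and one subsequent 76mg/1.9mL vial after the second 44mg/1.1mL vial". The first limb of Group C is "only one 44mg/1.1mL vial prior to receiving a 76mg/1.9mL vial". The note beneath reads "Note that patients who received only 44mg/1.1mL vials or only 76mg/1.9mL vials are not classified under any SUD exposure group", and adds that these patients stay in the study population.

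Section 8 states that the objectives are assessed in MM patients receiving elranatamab. It does not restrict them to patients who completed step-up.

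**The concern.** CRS and ICANS are looked for in the first 14 days. Whether a patient goes on to a 76mg vial is settled after index and may depend on what happened in those days. A patient who has CRS or ICANS after a 44mg vial and never receives a 76mg vial leaves both numerator and denominator. The reported incidence then describes patients who got through step-up, while a reader of this post-authorisation safety study will take it as the incidence among initiators.

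Nothing elsewhere restores these patients. Section 9.7.6 plans no sensitivity analysis, Section 9.9 does not list the restriction as a limitation, and the low-weight subgroup in Section 9.7.5 repeats Objective 5 and inherits the gap.

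**Working it through.** The protocol states no event rate or power figure on this point, so there is no figure to reproduce. The check traces the definitions and then illustrates size under stated assumptions.

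**1. Does every group need a 76mg vial?**
- Groups A and B: yes, in Table 1.
- Group C, one 44mg vial, and Group C, more than two: yes. Both are defined as preceding a 76mg vial.
- Group C, extremely untimely: the first limb in Table 1 (over 14 days between the two 44mg vials) does not mention a 76mg vial. Table 12 lists one for this row, and the Table 1 note excludes 44mg-only patients from every group. So yes.

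**2. Who is left out?** Patients with only 44mg vials and patients with only 76mg vials. Table 4 counts both types under Objective 2, so the plan expects them.

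**3. Is the restriction forced by the windows?**
- CRS/ICANS: no. Section 9.2 runs the 14 days from index and shortens them to the data available, so every patient has a window.
- IVIG: no. The 30-day window is built the same way.
- Cytopenias, dexamethasone, diphenhydramine, acetaminophen, tocilizumab: yes. The SUD period opens at the first 44mg vial and closes at the first 76mg vial. It has no end for 44mg-only patients and no start for 76mg-only patients.

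**4. When is membership known?** Group B allows up to 14 + 14 = 28 days from the first 44mg vial to the first 76mg vial, and Group C can be longer. Membership can therefore be settled after the 14-day outcome window has closed.

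**5. Size (illustration).** Let f be the unclassified share, r_c the risk in classified patients and r_u the risk in unclassified patients.
- All-patient risk = (1 − f)·r_c + f·r_u
- Shift from the reported figure = f·(r_u − r_c)

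The only documented input is 128 patients with a claim at the February 2025 cut (Section 9.5). Assumed: f of 5%, 10% and 20%; CRS r_c = 50%, r_u = 50-90%; ICANS r_c = 3%, r_u = 3-30%.

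| f (left out / classified) | CRS, all patients (reported 50.0%) | ICANS, all patients (reported 3.0%) |
|---|---|---|
| 5% (6 / 122) | 50.0-51.9% | 3.0-4.3% |
| 10% (13 / 115) | 50.0-54.1% | 3.0-5.7% |
| 20% (26 / 102) | 50.0-58.1% | 3.0-8.5% |

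Upper ends at f = 10%:
- CRS: (115 × 0.50 + 13 × 0.90)/128 = 69.2/128 = 54.1%.
- ICANS: (115 × 0.03 + 13 × 0.30)/128 = 7.35/128 = 5.7%. Here 3.9 of 7.35 cases (53%) go uncounted.

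At equal risk the ICANS proportion does not move, but 0.39 of 3.84 cases (10%) are still uncounted.

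**The case against.** **Objective 5 is worded around the SUD period, which does not exist without both vial sizes.** This has force for cytopenias and the SUD-period medications, where a row alone would not be enough. It does not cover CRS and ICANS, which Tables 2 and 7 place in a window that needs no 76mg vial.

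**The abstract suggests that an overall result was intended.** It says SUD-period outcomes will also be stratified, by "complete and timely SUD, complete but not timely SUD, alternative SUD". That may well be the intention, but Table 2 contains no overall row and Section 9.7 defers to Table 2. The two need reconciling.

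**The effect is unproven and may be smaller than sampling error.** Direction and size are indeed not established. In the 10% illustration the largest CRS shift is 4.1 points, against a 95% half-width of 1.96 × √(0.5 × 0.5/115) = 9.1 points. For ICANS it is 2.7 against 1.96 × √(0.03 × 0.97/115) = 3.1 points. Sampling error, however, does not justify leaving out known cases whose data are already in hand.

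**The scope is narrow.** Objective 5 is secondary and descriptive, with no comparison between groups planned. The exclusion is disclosed, and infections (Objective 6) use the whole study population. All of this stands.

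Two stronger readings are tempting and are not supported. A reader might infer that 44mg-only patients are those who stopped or died in step-up. Section 9.2 says a 44mg vial may also be a partial dose, and others may still be in step-up at the data cut or, given the limits in Section 9.9, have moved hospital. A reader might also infer that IVIG is lost for these patients. Only the 30-day row is, because Objective 4 reports IVIG over follow-up for the study population.

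**Conclusion.** The gap is real and follows from the definitions alone. As written, a patient with only one vial size contributes to no CRS, ICANS, cytopenia or SUD-period supportive-medication estimate, nor to the 30-day IVIG row. This conflicts with the population named in Section 8 and conditions the results on a post-index event that CRS or ICANS may prevent.

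It does not follow that the reported incidence will be too low. That holds only if the unclassified patients have higher risk. Under the assumed ranges (f of 5-20%) the understatement runs from 0 to 8.1 points for CRS and from 0 to 5.5 points for ICANS. The documents give neither the number of unclassified patients nor any risk, so these figures show scale and are not estimates.

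The absence of Group B as its own row, although the abstract names it as a stratum, is a minor presentation point. Its counts follow from A+B minus A, though medians and quartiles do not.

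**What to change.** 1. In Table 2, add a Study population row as the lead result for CRS/ICANS over the existing 14-day window and for IVIG over the existing 30-day window. A population restricted to patients who start on a 44mg vial would not suffice, because it still omits 76mg-only initiators.
2. Add a row for unclassified patients, with 44mg-only and 76mg-only shown apart, and keep Groups A, A+B and C as secondary results.
3. For cytopenias and the SUD-period supportive medications, also report a window fixed from index, for example the existing 14 days, so that patients without an SUD period have a defined observation time.
4. Optionally, list Group B separately to match the abstract.

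Items 1, 2 and 4 are extra rows from data already held. Item 3 costs a small change to the variable definitions in Tables 7 and 9 and to the wording of Objective 5 and Exploratory Objective 1. None of this touches dosing or clinical management.

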9.2. Setting

The study population will be extracted from MDV, a comprehensive resource based on hospital claims data and Diagnosis Procedure Combination (DPC) data. Information on demographics, mortality, laboratory tests, IP, OP, and ED claims, treatments, procedures, and costs are available for approximately 50 million patients. Patients will be identified using the inclusion and exclusion criteria listed in Sections 9.2.1 and 9.2.2. The inclusion and exclusion criteria ensure the study captures patients with MM who initiate elranatamab treatment in RW setting after its approval date in Japan. The exclusion criterion removes patients treated within clinical trials to avoid bias from controlled study conditions and ensure generalizability to routine clinical practice. These criteria may limit the number of eligible patients, especially early in the elranatamab post-approval period.

Index date: defined as the date of first hospital claim with elranatamab administration after March 26, 2024.

44mg/1.1mL vial of elranatamab: hospital claim of elranatamab with vial size of 44mg/1.1mL which corresponds to an SUD dose or a partial dose.

76mg/1.9mL vial of elranatamab: hospital claim of elranatamab with vial size of 76mg/1.9mL which corresponds to a full dose.

Study period: defined as the period between start of data availability to end of data availability in MDV.

Baseline period: defined as the variable period between MM diagnosis and first hospital claim of elranatamab administration (index date).

Medical history assessment window: defined as the 365-day window prior index date. If a patient has fewer than 365 days of data available prior to the index date, the assessment window will be equal to the maximum number of days available prior to the index date.

CCI assessment windows: defined as (1) the 180-day window prior index date and (2) the 365-day window prior to index date. If a patient has fewer than 180 days, or 365 days of data available prior to the index date, the assessment window will be equal to the maximum number of days available prior to the index date.

HCRU baseline assessment period: defined as the 180-day window prior index date. If a patient has fewer than 180 days of data available prior to the index date, the assessment window will be equal to the maximum number of days available prior to the index date.

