9.7.3. Relative Administration Intensity

RAI will be calculated as the cumulative frequency of administration received over the expected number of administrations. Since response is needed to determine if switching to bi-weekly doses is appropriate and is not available in MDV, two schedule definitions will be used to estimate the expected number of administration to calculate RAI (Table 10. Dosing Schedule of Elranatamab during Follow-up Period for Patients Switching to

Q2W and Table 11. Dosing Schedule of Elranatamab during Follow-up Period for Patients staying on

QW Table 10. Dosing Schedule of Elranatamab during Follow-up Period for Patients Switching to

Q2W).

$$\text{RAI} = \frac{\text{Number of administrations received}}{\text{Number of expected administrations during the time period}}$$

a) Schedule 1¹

Assumption that all patients switch to bi-weekly doses (Q2W) after day 169 post-index.

Table 10. Dosing Schedule of Elranatamab during Follow-up Period for Patients Switching to Q2W

Follow-up Sub-Periods	Expected Administrations	Vial Size
Index date - Day 8	3 administrations	2 x 44mg/1.1mL 1 x 76mg/1.9mL
Day 9 - Day 168	1 administration per week	76mg/1.9mL
Day 169 – End of follow-up	1 administration every two weeks	76mg/1.9mL

Notes:

090177e1a4a71ff1\Approved\Approved On: 05-Nov-2025 14:15 (GMT)

¹ Adapted from dosing and administration guidance of the Japanese elranatamab label available at <https://labeling.pfizer.com/ShowLabeling.aspx?id=20462>

b) Schedule 2¹

Assumption that all patients continue with weekly doses (QW) after day 169 post-index.

Table 11. Dosing Schedule of Elranatamab during Follow-up Period for Patients staying on QW

Follow-up Sub-Periods	Expected Administrations	Vial Size
Index date - Day 8	3 administrations	2 x 44mg/1.1mL 1 x 76mg/1.9mL
Day 9 – End of follow-up	1 administration per week	76mg/1.9mL

Notes:

¹ Adapted from dosing and administration guidance of the Japanese elranatamab label available at <https://labeling.pfizer.com/ShowLabeling.aspx?id=20462>

Treatment exposure will be assessed across the different follow-up periods. End of follow-up is defined as the end of the hospital claim of the last elranatamab administration inclusive.

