9.9. Limitations of the Research Methods

This study is subject to limitations, described below:

- The MDV database follows patients' medical journey through the same facility, not between facilities – as such there is visibility only on prior diagnoses received within the same facility. There may be a loss in data continuity due to hospital transfers, however, patients in Japan tend to be treated in the same centers therefore this may be minimal.
- Measures of MM disease severity, such as ISS stage, M-protein level, and cytogenetic risk are not available in MDV. This limits the extent to which patients' MM can be characterized.
- This study will use a secondary data source. Because of the secondary data source, common limitations apply to this study, including:
 - Data may not be complete or accurate due to potential errors in coding or record-keeping at the point of the healthcare provider.
 - Lags in data availability can lead to inaccuracies in timing of reported information. This can particularly impact estimates over short periods of time (e.g., HCRU on index date).
 - Missing data cannot confirm the absence of a condition or value in a patient's medical history; only that it was not documented.
 - The internal process of obtaining and cleaning data is not fully known by scientists using RW databases, as such the internal validity of RWD remains largely unknown to scientists working with the data (19). Although there are concerns about the validity of RWD, the MDV database still has been used for a large number of peer-reviewed publications (14).
 - The lack of granularity of certain variables can limit the research that can be done; for example, granularity of grade of infection is often not available.
 - Clinical trials have close monitoring and prospective data collection, which RWD lacks. This means that the description of AEs in RW patients is expected to be less precise. Additionally, estimates of incidence and prevalence of safety events are likely to be underestimated compared to clinical trials or prospective studies where timing of assessments can be controlled. However, RWD can be useful to describe incidences of AEs in a larger and more heterogenous samples (20).
- This study population consists Japanese patients treated with elranatamab in Japan; however, the data does not cover all patients in Japan. As such, results may not fully represent the broader experience of patients receiving elranatamab both within Japan and internationally.

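### Day 1 is the first MDV elranatamab claim of any vial size, so patients stepped up at another hospital are indexed late and pooled with those who truly started on a 76 mg vial

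*Protocol*

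**What the plan says.** - **Entry and index.** Protocol 9.2.1 admits patients by "First hospital health claim with an administration of elranatamab on or after March 26, 2024". Section 9.2 gives the index date as "defined as the date of first hospital claim with elranatamab administration after March 26, 2024". Neither requires the index vial to be a 44 mg vial, and neither requires a minimum look-back.
- **Meaning of the vials.** Section 9.2 describes the larger vial as a "hospital claim of elranatamab with vial size of 76mg/1.9mL which corresponds to a full dose". A 44 mg claim is either a step-up dose or a partial dose.
- **Unclassified patients.** The note to Table 1 (9.3.1) says that patients with only 44 mg vials or only 76 mg vials fall in no step-up group "but will remain part of the study population". Table 2 uses that population for the follow-up results of Objectives 2, 3, 4 and 6.
- **Data source.** Section 9.9 says that MDV follows the "medical journey through the same facility, not between facilities". It adds that "patients in Japan tend to be treated in the same centers therefore this may be minimal".
- **RAI.** The denominator in 9.7.3 is the "Number of expected administrations during the time period". Tables 10 and 11 expect three administrations by day 8 for every patient (two 44 mg, one 76 mg), then one per week. Under Schedule 1 the change to every two weeks is counted from the index date.
- **Other handling.** Table 4 counts patients with only 76 mg vials. Section 9.7.6 plans no sensitivity analysis.

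**The concern.** The research question is about patients who initiate elranatamab. By the protocol's own definitions, a first recorded claim for a 76 mg vial has two explanations: step-up was given at a hospital that MDV cannot link, or there was no step-up. The protocol has no rule to tell these apart and treats both as starting on day 1.

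In the first case the recorded day 1 is not the start of treatment. Duration (first to last administration) is too short, days from index to first infection start late, and every sub-period boundary, including day 169, is shifted. The 180-day HCRU baseline may cover time already on treatment. RAI is also charged for step-up doses that were given but are not visible. Duration and RAI belong to Objective 2, a primary objective.

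**Working it through.** The only sample figure, 128 patients in the February 2025 data cut, is an observed count, so there is no sample size calculation to reproduce. The check is on the RAI denominator.

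**Inputs.** Tables 10 and 11 give three doses in day 1-8, weekly doses to day 168, then every two weeks (Schedule 1) or weekly (Schedule 2). The day of the second 44 mg dose is not given in those tables; day 4 is assumed, and this does not affect the counts.

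**Expected doses on the protocol's schedule.** Doses fall on days 1, 4, 8, then 15, 22, ..., 162.
- Day 1-8: 3.
- Day 9-168: (162 − 15)/7 + 1 = 22 (a pure rate, 160/7, gives 22.9).
- Day 1-168: 3 + 22 = 25.

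A fully adherent patient indexed at the true first dose scores 1.00 in each sub-period.

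**The same adherent patient, first seen in MDV at a later 76 mg dose.** RAI = recorded doses / expected doses.

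| First MDV claim | Schedule followed | Day 1-8 | Day 9-168 | Day 1-168 | Duration short by |
|---|---|---|---|---|---|
| True day 8 | 1 or 2 | 2/3 = 0.67 | 22/22 = 1.00 | 24/25 = 0.96 | 7 days |
| True day 85 | 1 | 2/3 = 0.67 | 16/22 = 0.73 | 18/25 = 0.72 | 84 days |
| True day 169 | 1 | 1/3 = 0.33 | 11/22 = 0.50 | 12/25 = 0.48 | 168 days |
| True day 85 or 169 | 2 | 2/3 = 0.67 | 22/22 = 1.00 | 24/25 = 0.96 | 84 or 168 days |

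Under Schedule 2 the RAI error is always one dose, however late the index. Under Schedule 1 it grows, because the patient changes to two-weekly dosing at true day 169 while the denominator stays weekly until recorded day 168.

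**Short follow-up.** For a weekly patient first seen on 76 mg, overall RAI is 2/3 = 0.67 if the last dose is on recorded day 8, 5/6 = 0.83 on day 29, and 13/14 = 0.93 on day 85.

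**Effect on the pooled mean.** Let q be the share of patients indexed late on weekly 76 mg doses, with all others at 1.0. The share is not in the protocol, so a range of 2% to 20% is assumed.
- Day 1-8 mean = 1 − q/3: 0.993 (2%), 0.983 (5%, about 6 of 128), 0.967 (10%), 0.933 (20%).
- Day 1-168 mean, if first seen on true day 8, = 1 − q/25: 0.998 (5%), 0.996 (10%), 0.992 (20%).

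**A 76 mg claim before a 44 mg claim.** The SUD period in 9.2 runs from the first 44 mg vial to the first 76 mg vial. If the 76 mg claim comes first, the end precedes the start. The Table 1 note does not cover this patient, because it addresses only patients with a single vial size.

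**The case against.** The strongest reply is that a 76 mg vial at the index date does not prove an earlier start. A patient who truly began on that vial has the right index and duration, and an RAI below 1 is then a real departure from the expected schedule, which Objective 2 exists to describe. Removing such patients would hide off-schedule use and select those who conform. This stands, and it rules out simply dropping them.

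Further points also stand in part:
- A day 1-8 RAI of 2/3 is not specific to late indexing. A Group A patient dosed on days 1, 8 and 15 is complete and timely by Table 1, yet also scores 2/3. A mean computed with all others at 1.0 is therefore illustrative only.
- A 44 mg claim can be a partial dose, so a 44 mg vial at the index date does not prove initiation either.
- SUD-period, CRS, ICANS, cytopenia and supportive-medication results use Groups A, A+B and C, which already exclude patients with only 76 mg vials. Among time-from-index outcomes, mainly infection is affected.
- Section 9.9 discloses the single-facility limit and suggests that the loss is small. It does not connect that limit to index date, duration or RAI. The count in Table 4 does not separate these patients in those results.

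A reader might also infer that a patient with 76 mg first and 44 mg later falls in no exposure group. That is too strong: the sequence 76-44-44-76 can literally meet Group A. The backward SUD period remains a defect.

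**Conclusion.** The point holds conditionally. Where step-up was given at another facility, the index is late and RAI, duration and time to infection are distorted. Where the patient truly started on 76 mg, they are not. The defect is that the protocol pools the two and plans nothing that would show the difference.

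It is tempting to conclude that all 76-mg-first patients are prevalent users with a misdated index. The protocol does not support that, since its definitions allow either explanation and it gives no share for either.

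For a single on-schedule patient the RAI error runs from one dose in 25 over day 1-168 to about half the expected doses after a late transfer under Schedule 1. On the pooled mean it is probably small: about 0.98 for day 1-8 at an assumed 5%, with everyone else at 1.0. These figures assume full adherence and, for the large errors, an actual change to two-weekly dosing at true day 169. The study is descriptive and makes no group comparisons, so the harm is to interpretation of the estimates.

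**What to change.** 1. Flag each patient by the vial size of the first MDV claim.
2. Keep the full study population for the main description. Report RAI, treatment duration, follow-up HCRU (including any sub-period results) and days from index to infection separately for 44-mg-first and 76-mg-first patients. Alternatively, replace the statement in 9.7.6 with a sensitivity analysis restricted to 44-mg-first patients.
3. Note beside these results that a 44 mg claim can also be a partial dose, so the flag is an imperfect marker of initiation.
4. State in 9.2 and Table 1 how a patient with a 76 mg claim before any 44 mg claim is assigned to a group, and how the SUD period is derived for that patient.
5. In 9.9, link the single-facility limitation to index date, duration and RAI.

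The cost is one flag derived from data already held, a little extra analysis, and strata that may be small. No patient is lost from the main tables and no clinical rule changes.
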